Study participants will be recruited starting with index cases that are identified through a Case report/Case investigation system. After a laboratory confirmed index case is identified at a health facility, the health worker completes an Immediate Notification Form investigation (Appendix B) and reports the case through the country's toll-free Immediate Disease Notification System (977). The NMCP Surveillance Team is notified by an SMS text. A Surveillance Agent visit the health facility to collect the DBS, RDT, and slide, and visits the home of the index case within 48 hours and to administer a questionnaire and capture GPS coordinates, as part of the case investigation (Appendix C). Also, if a DBS was not collected by the health facility at the time of presentation, the surveillance agent also collects a DBS.

If the index case resides in a study locality, that neighborhood or Target Area will become enrolled in the study. During intervention resident enrollment, the study staff will begin recruiting study participants from the home of the index case, and then move on to neighboring households. On the first visit, the team will map the location of the index case and visualize the 200 or 500 meter radius on google maps while in the field. The team will attempt to enroll all individuals residing within 200 or 500 meters, depending on whether that Target Area has been randomized to receive TPE or RACE. On the second visit, the team must come at a time during which persons previously absent will be present (usually morning or late afternoon/early evening) and re-visit all households in which 100% coverage was not achieved. If 100% coverage is obtained, that Target Area intervention is complete. If not, on the 3rd visit, the team must also come at a time during which persons previously absent will be present (usually morning or late afternoon/early evening) and the study team must re-visit households in which 100% coverage was not achieved. If during this 3rd visit 30 individuals are not yet enrolled (participated in study intervention), the team will move onto the next closest house (but not beyond 500m) to screen individuals until at least 30 individuals are enrolled (but completing the screening in all individuals in that last household).

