14.1 Study population

Overall:

Based on the most recent census data, the overall population in the 77 study localities is estimated at 211,189 individuals. However we expect that some localities will have no incident cases and therefore not receive any intervention. In the previous two transmission seasons, only 63 of the 77 localities had at least one case. Our sample size calculations are further based on the expected at-risk population within the 63 localities, or EA that had at least one case in the previous three seasons, a total of 55,928 individuals. The size of the expected at-risk within localities varies greatly, therefore we used the harmonic mean of

population size in localities with at least one case (656 per locality) to represent the effective sample size of the study in calculations of the design effect.

Target Area:

As defined above in section 4.4, the Target Area for TPE localities is defined as all individuals residing within 200m of an index case that is detected in passive surveillance and resides in a TPE study locality, with individuals residing immediately beyond 200m included if a minimum of 30 enrolled individuals is not reached within 200m. The Target Area for RACD localities is defined as all individuals residing within 500m of an index case that is detected in passive surveillance and resides in a RACD study locality. Sample size calculations for the secondary outcome measures of seroprevalence and infection prevalence are based on the population of the Target Areas.

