14.2 Outcome measures

Table 6. Outcome measures

Outcome	Indicator
Primary Aim	
Incidence	Cumulative incidence of all cases (Pf infection) identified by passive surveillance in the locality subsequent to the first reported case during the study period (not including additional cases found through RACD). Cases include both locally acquired and imported infections.
Secondary aims (effectiveness)	
Exposure (seroprevalence)	Seroprevalence to markers of recent exposure using ELISA in end-line survey samples taken from residents in Target Areas near the end of the study (expected mid 2017), excluding index cases detected through passive surveillance.
Infection prevalence	Prevalence of infection by LAMP and QTNASBA testing for gametocytes in LAMP positives in end-line survey samples taken from residents in Target Areas near the end of the study (expected mid 2017), including index cases detected through passive surveillance.
Time to first local post-intervention incident case	Time to first incident local case in the Target Area subsequent to the intervention. Target Areas that receive a repeat intervention will qualify to be included again at subsequent interventions.
Proportion of imported incident cases	Proportion of imported incident cases in the locality subsequent to the first reported case will be measured through passive surveillance. Additional cases found through RACD will not be included.
Transmission potential (by genotyping)	Microsatellite genotyping will be performed on samples collected from index cases as well as secondary cases.
Secondary aims (feasibility)	
Coverage	Proportion of persons residing within approximately 200m (TPE localities) or 500m (RACD localities) of the index case who consented to participate in the study and who completed the initial procedures for their study arm (finger prick for RDT in the RACD arm, initial dose of DP in the TPE arm)
Adherence	Proportion of persons who completed 3 days of therapy among all individuals initiated on DP in the TPE arm, as assessed by pill count
Prevalence of SAEs related to treatment	Proportion of subjects experiencing SAEs deemed possibly, probably, or definitely related to DP or AL, out of the total number of subjects enrolled
Acceptability	Qualitative assessment (See Section 10)
Cost	Cost per index case-level intervention, cost per case averted.

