Based on equation 4 from Hayes and Bennett International Journal of Epidemiology 1999;28:319-32

Assumes that population is only those in the EAs that have at least one case.

Sample size calculation based on harmonic mean of population size.

Table 8. Detectable reductions in seroprevalence given varying assumptions about prevalence in the RACD arm

# Total localities with at least one index case	# localities per arm	Number assessed per locality (n)		Outcome proportion		Km (coeff of variation)	Z beta	Power
		RACD	TPE	RACD (π_0)	TPE (π_1)			
46.6	23.3	60	60	3.00%	1.35%	0.9	0.84	80%
62.3	31.2	60	60	2.40%	1.18%	0.9	0.84	80%
49.3	24.7	60	60	2.00%	0.83%	0.9	0.84	80%
50.8	25.4	60	60	1.50%	0.57%	0.9	0.84	80%

Based on equation 4 from Hayes and Bennett International Journal of Epidemiology 1999; 28:319-326

Assumes we are including only persons in the target areas in the denominator but evaluating at locality level

Assumes 3 per 100 is the background seroprevalence

Table 9. Sample sizes for primary and secondary aims.

Outcome	Result*	Actual sample size (Effective sample size, based on harmonic mean in clusters)
Primary aim		
Incidence	0.4% (RACD) vs. 0.2% (TPE)	55,928 (41,328)
Secondary aims (effectiveness)		
Exposure (seroprevalence)	2.4% (RACD) vs. 1.18% (TPE)	5400 not including index cases (3720)
Infection prevalence	n/a	5600 includes index cases
Time to first post-intervention incident case	n/a	55,928 (41,328)

Outcome	Result*	Actual sample size (Effective sample size, based on harmonic mean in clusters)
Proportion of imported incident cases	n/a	55,928 (41,328)
Transmission potential	n/a	Genotyping estimated to be performed in 800 index cases** and 35 infections from follow-up cross sectional survey
Secondary aims (feasibility)		
Coverage in TPE Arm	80% (95% CI: 77%-83%)	1782
Adherence in TPE Arm	80%	532
Prevalence of SAEs related to treatment	n/a	5400 not including index cases (3720)
Acceptability	n/a	5400 not including index cases (3720)
Cost	n/a	10 Target Areas/arm

*for some secondary outcomes, power calculations were not performed however effective sample size is shown.

** 200 index cases will be from the study area but an estimated 600 DBS that are already collected as standard surveillance from other parts of the country will also be used to characterize the background genotypes/transmission potential in Swaziland, as it relates to the transmission potential in the study areas.

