4. Comparison of time to first post-intervention incident infection. We hypothesize that time to the first post-intervention index case within the Target Area will be longer for Target Areas receiving TPE compared to those receiving RACD. Analysis for this outcome will use a standard cox proportional hazards model to estimate the time to a subsequent incident infection among individuals in the Target Area.
5. Comparison of transmission potential using genotyping. Microsatellite genotyping will be used to measure transmission potential. DNA samples for genotyping will be collected from index cases and secondary cases. Based on malaria rates in Swaziland over the past three years, we expect approximately 200 index cases over the study period and 35 infections from the follow-up cross sectional survey (1.6% prevalence in the TPE arm and 0.4% in the RACD arm). We expect transmission potential to be lower in the TPE versus RACD arm. Relatedness of infections within Target Areas and within localities will be used as a surrogate for transmission potential.

Planned Analyses of Operational Feasibility and expected findings:

1. Coverage of the intervention. The numbers and proportion of the population completing finger prick testing (if RACD arm) or receiving at least the first dose of medication (if TPE) will be calculated by arm. The proportion of the individuals living in Target Areas around an index case that receive the TPE intervention is expected to be 80% with a 95% confidence interval from 76% to 84%.
2. Adherence to TPE. In the subsample of Target Areas surrounding the first index case in each locality assigned to TPE, we will assess adherence to the 3 day regimen of DP in TPE using pill count. We expect adherence to be 80%.
3. Safety of the TPE treatment. The number and percent of individuals experiencing an adverse event will be recorded by study arm. We expect that compared to RACD, TPE will be safely administered with few or no serious adverse events related to treatment, and no difference in SAEs compared to AL based on analysis of the adverse events report forms.
4. Acceptability of the intervention. See Section 10.
5. Costs per incident infection and per population. Detailed costing will be performed in 10 Target Areas per arm. We expect that costs per incident infection and per population for implementing the TPE intervention will be no higher than for RACD, the current standard of care.

15 Advisory Committee

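### Three secondary effectiveness outcomes are compared over different areas by arm (200 m in TPE, 500 m in RACD), and the definition of time to first local case needs tidying

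*Combined protocol and SAP*

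**What the plan says.** **Areas.** Section 14.1 defines the two arms differently. For TPE, "the Target Area for TPE localities is defined as all individuals residing within 200m of an index case", with "individuals residing immediately beyond 200m included if a minimum of 30 enrolled individuals is not reached within 200m". For RACD, "The Target Area for RACD localities is defined as all individuals residing within 500m of an index case that is detected in passive surveillance". Section 6.2 limits the extension: "the team will move onto the next closest house (but not beyond 500m) to screen individuals until at least 30 individuals are enrolled".

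**Outcomes.** Section 9.3 invites all residents of Target Areas to the end-line survey. Table 6 (Section 14.2) takes seroprevalence and infection prevalence from those residents. It defines the third outcome as "Time to first incident local case in the Target Area subsequent to the intervention", and adds that "Target Areas that receive a repeat intervention will qualify to be included again at subsequent interventions".

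**Distance.** Section 1.3 reports an odds ratio for infection of 4.6 (95% CI 2.0 to 10.6) within 100 m of the index case against 201-500 m. Section 14.4 adjusts secondary models for distance to the nearest TPE-treated index case.

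**Time to first case elsewhere.** The hypothesis in Section 14.4 is about Target Areas, but it refers to the first later index case. The model sentence then names a "standard cox proportional hazards model to estimate the time to a subsequent incident infection among individuals in the Target Area". Earlier in the same section, Target Area outcomes are said to account for clustering by locality and by index case area. In Table 9 the row "Time to first post-intervention incident case" carries 55,928 (41,328).

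**The concern.** The radius is part of the outcome's denominator as well as of the intervention. If risk falls with distance from the index case, a survey that reaches out to 500 m in one arm and mostly 200 m in the other compares populations of different risk, even when the two interventions work equally well. Randomisation cannot balance a difference that is written into the definition.

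The planned covariate does not help. It is there for contamination. For a TPE resident it will usually be the distance to their own index case. For an RACD resident it is the distance to a case assigned to the other arm.

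For time to first case the effect runs the other way: a larger area holds more people, so its first later case tends to come sooner. Three secondary effectiveness comparisons could therefore show, or hide, a difference that is not an effect of TPE. No passage sets a common analysis radius.

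**Working it through.** **1. The plan's own figure.** The expected at-risk populations of the 63 localities with cases in Table 2 sum to 55,928. Their harmonic mean is 656.3, and 63 × 656 = 41,328. This reproduces the Table 9 entry and shows that it is the locality at-risk population. The Target Area sample is 200 × 30 × 0.9 = 5,400 (Section 14.1).

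**2. Inputs for the size of the bias.**
- Ring areas for 0-100, 100-200 and 200-500 m are in the ratio 1 : 3 : 21, since 1² : (2² − 1²) : (5² − 2²).
- Relative risk is r = 4.6 within 100 m (Section 1.3) and 1 at 201-500 m. The odds ratio is used as a risk ratio; at 0.9% positivity 4.6 becomes about 4.5.
- The text gives no risk for 101-200 m, so x is assumed anywhere from 1 to 4.6.
- Mean risk within 200 m is M = (r + 3x)/4, so from (4.6 + 3)/4 = 1.9 to 4.6.

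**3. Survey outcomes, no true effect.** Let s and t be the shares of RACD and TPE respondents living beyond 200 m. The plan gives neither. The TPE/RACD ratio is [(1 − t)M + t] / [(1 − s)M + s].

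| s (RACD) | t (TPE) | M = 1.9 | M = 4.6 |
|---|---|---|---|
| 0.25 | 0 | 1.90/1.675 = 1.13 | 4.60/3.70 = 1.24 |
| 0.25 | 0.10 | 1.81/1.675 = 1.08 | 4.24/3.70 = 1.15 |
| 0.50 | 0 | 1.90/1.45 = 1.31 | 4.60/2.80 = 1.64 |
| 0.50 | 0.25 | 1.675/1.45 = 1.16 | 3.70/2.80 = 1.32 |
| 0.10 | 0.25 | 1.675/1.81 = 0.93 | 3.70/4.24 = 0.87 |
| s = t | | 1.00 | 1.00 |

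With r at its confidence limits (2.0 and 10.6), the 25% case spans 1.03-1.29 and the 50% case 1.06-1.83. The planned seroprevalence contrast is 1.18/2.4 = 0.49. If that were true, it would read 0.53-0.61 in the 25% case and 0.57-0.81 in the 50% case.

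The range for t is consistent with the plan. A simulation used a mean of 53 residents within 200 m (Section 4.4), an assumed coefficient of variation of neighbourhood size of 0.3-1.0, and filling up to 30. It puts 9.9-25.3% of those enrolled beyond 200 m at 60% enrolment, and 2.6-17.0% at 80%.

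**4. Time to first local case, Target Area as unit, no true effect.** Later cases come from passive surveillance, so everyone in the area counts, not only those surveyed. Let g be outer-ring population density relative to inner (assumed 0.25 to 1) and I = r + 3x (7.6 to 18.4). A TPE share t beyond 200 m adds 4t/(1 − t) outer units, which is 1.33 at t = 0.25. Then HR = [I + 4t/(1 − t)] / (I + 21g).
- t = 0: 7.6/28.6 = 0.27 (g = 1) to 18.4/23.65 = 0.78 (g = 0.25).
- t = 0.25: 8.93/28.6 = 0.31 to 19.73/23.65 = 0.83.

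The range is about 0.27-0.83, in favour of TPE. The share of RACD events arising beyond 200 m is 1 minus the t = 0 values, or 22-73%.

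**5. The same outcome read as an individual-level model.** The formula in step 3 applies with s = 21g/(4 + 21g), which is 57-84%. At t = 0 the null HR is 1.37-2.92, and at t = 0.25 it is 1.21-2.35. The direction is reversed.

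**6. Precision under a 200 m restriction.** With Table 8 inputs (60 per locality, k = 0.9, 2.4% and 1.18%), the variance is p0(1 − p0)/n0 + p1(1 − p1)/n1 + 0.81(p0² + p1²). Relative to n0 = n1 = 60, the standard error is multiplied by 1.054 at (n0, n1) = (45, 60), 1.063 at (45, 54), 1.156 at (30, 60) and 1.179 at (30, 45).

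**The case against.** **The areas may differ less in practice than on paper.** Section 4.4 tells RACD teams to concentrate on the inner 200 m and computes past coverage as 32 of 53 residents within 200 m. Section 14.1 plans 30 people per index case whichever the arm. This stands as a reason to put more weight on the lower survey values. It does not change who is invited at end-line or which later cases count.

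**RACD at 500 m is the policy being compared.** That is true, and the locality-level primary outcome reflects it properly. It does not justify unequal denominators for outcomes defined within the area.

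**The gradient is borrowed.** It is LAMP positivity at reactive visits, Figure 3 is not available in the text, and no distance gradient for serology is given. This stands: the sizes are illustrations over stated ranges. Only seroprevalence has a powered target, so 0.49 is not a benchmark for the other two outcomes.

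**Stronger readings that the documents do not support.**
- A reader might infer that time to first case has three rival estimands. Table 6 and the hypothesis in Section 14.4 both make the Target Area the unit. Table 9 is a sample-size table, and its footnote says that some rows only show an effective size. The phrase about individuals is ambiguous and may only say where the infection occurs.
- A reader might infer that the Cox model will ignore clustering and give p-values that are too small. The general clustering statement in Section 14.4 can cover it, and the k of 0.9 was derived for proportions. The gap is one of specification.
- A reader might infer that the survey bias always runs against TPE. It depends on the two shares.

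**Conclusion.** The point holds for three secondary effectiveness outcomes and should be fixed before analysis. The unequal radii are written into the outcome definitions, and nothing in the plan corrects for them.

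For the surveys, a modest imbalance (25% of RACD and 0-10% of TPE respondents beyond 200 m) gives a null ratio of about 1.08-1.24. Larger RACD shares give more, 1.16-1.64 at 50% of RACD and 0-25% of TPE. For time to first local case per Target Area, the null HR of about 0.27-0.83 favours TPE under the assumed densities. These figures rest on the shares, the densities, the 101-200 m risk and the carry-over of the visit-time gradient to later outcomes, none of which the documents supply.

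Four smaller matters concern time to first case only. The wording about individuals is ambiguous, and an individual-level reading would reverse the bias. Section 14.4 drops Table 6's restriction to local cases. The Table 9 entry does not match a Target Area outcome. The Cox specification that would meet the clustering statement is not given.

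**What to change.** Leave the intervention radii as they are. In Table 6 and Section 14.4:
1. Make the main between-arm comparison of the three outcomes among residents, and later local cases, within 200 m of the index case in both arms, using GPS. Report the full arm-specific Target Areas as supplementary.
2. For time to first case, state the Target Area as the unit and a local case as the event, and correct the Table 9 row.
3. Set one analysis rule, the same in both arms, for linking overlapping areas and for repeat entry. A 200 m filter alone does not equalise these. Neighborhood IDs are reused within 500 m in RACD (Appendix H) but within 200 m in TPE (Appendix J). Section 4.4 bars a repeat within 5 weeks in RACD, and within 8 weeks or more than twice in a year in TPE. This concerns the analysis only, not the re-intervention rules.
4. Specify a Cox model with locality-clustered, small-sample-corrected standard errors or a locality frailty, and make it cover repeat entries.

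**Cost.** The change is SAP wording and a filter on coordinates already collected. The seroprevalence standard error rises by about 5-6% if a quarter of RACD and 0-10% of TPE respondents are dropped, and by 16-18% if half of RACD and 0-25% of TPE are. Under the assumed densities, 22-73% of RACD area-level events leave the main time-to-case analysis. The main comparison no longer reflects RACD at 200-500 m. The supplementary analysis and the primary outcome still do.

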14.2 Outcome measures

Table 6. Outcome measures

Outcome	Indicator
Primary Aim	
Incidence	Cumulative incidence of all cases (Pf infection) identified by passive surveillance in the locality subsequent to the first reported case during the study period (not including additional cases found through RACD). Cases include both locally acquired and imported infections.
Secondary aims (effectiveness)	
Exposure (seroprevalence)	Seroprevalence to markers of recent exposure using ELISA in end-line survey samples taken from residents in Target Areas near the end of the study (expected mid 2017), excluding index cases detected through passive surveillance.
Infection prevalence	Prevalence of infection by LAMP and QTNASBA testing for gametocytes in LAMP positives in end-line survey samples taken from residents in Target Areas near the end of the study (expected mid 2017), including index cases detected through passive surveillance.
Time to first local post-intervention incident case	Time to first incident local case in the Target Area subsequent to the intervention. Target Areas that receive a repeat intervention will qualify to be included again at subsequent interventions.
Proportion of imported incident cases	Proportion of imported incident cases in the locality subsequent to the first reported case will be measured through passive surveillance. Additional cases found through RACD will not be included.
Transmission potential (by genotyping)	Microsatellite genotyping will be performed on samples collected from index cases as well as secondary cases.
Secondary aims (feasibility)	
Coverage	Proportion of persons residing within approximately 200m (TPE localities) or 500m (RACD localities) of the index case who consented to participate in the study and who completed the initial procedures for their study arm (finger prick for RDT in the RACD arm, initial dose of DP in the TPE arm)
Adherence	Proportion of persons who completed 3 days of therapy among all individuals initiated on DP in the TPE arm, as assessed by pill count
Prevalence of SAEs related to treatment	Proportion of subjects experiencing SAEs deemed possibly, probably, or definitely related to DP or AL, out of the total number of subjects enrolled
Acceptability	Qualitative assessment (See Section 10)
Cost	Cost per index case-level intervention, cost per case averted.

